	0.35	0.27	0.44	$\pm 8\%$
	0.40	0.32	0.49	$\pm 9\%$

Type I error of 0.05, two-tailed test

Sample Size Based on the Null Hypothesis & Error Rates:

We will also compare the primary efficacy outcome to that of historical controls. The eligibility criteria, baseline factors, clinical management protocols, criteria for NIV and MV, & outcomes in our study are similar to those of recently published clinical trials. The use of historic controls will decrease sample size, shorten duration, and enhance efficiency of our Phase II study; definitely an advantage for testing four dosing regimens in this orphan population^{1,90-94}. Additionally, since AS has been shown to be potentially beneficial, this will allow all patients to receive study medication early and non-invasively thus enhancing study feasibility.

The rate of intubation following NIV for RDS among 24-36 weeks GA PT infants is ~50%^{75,95}. We estimated a 50% relative risk reduction to be clinically significant and plausible based on our preliminary data & reports in literature. Studies of MIST during NIV in PT infants 24- 36 weeks GA with RDS show an absolute risk reduction of the need for MV of 10-50% and a relative risk reduction of 21-63% (RR 0.67, 95% CI 0.57, 0.79) with a lower treatment threshold (FiO₂≤0.45) conferring a greater advantage (RR 0.72, 95% CI 0.59, 0.87) compared to a higher threshold (FiO₂>0.45) (RR 0.55, 95% CI 0.40, 0.77)^{5,33,75,92,93,95-104}.

A sample size of 30 subjects within each dose schedule group will have 81.8% power to detect a relative risk reduction of 50% (absolute risk reduction 25%) in the primary outcome of the need for intubation in 72 hours compared to a historical control value of 0.5 in a two-tailed type I error rate of 0.05 (Table 13).

Collapsing dilution groups corresponding to dose of 100 mg/kg & 200 mg/kg or considering our entire sample of 120 subjects all of whom receive AS will allow us to detect a smaller effect size with greater power.

An alternative strategy for sample size of Phase II trials is to reduce the level of rigor required by increasing the Type I error rate to as large as 25%^{90,105}. This increases the risk of erroneously concluding that the treatment is worthy of further investigation but does not increase the risk of missing an efficacious treatment. This approach would allow us to evaluate the effect sizes in Table 13 with smaller sample sizes.

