Table 13: Power for a Test of the Null Hypothesis assuming a Historical Control Value of 0.5

Sample Size	Rate	Absolute RR	Relative RR	Power
30 (for each dosing Schedule I, II, III, IV)	0.25	.25	.50	81.8%
60 (for each dose group 100/kg vs 200 /kg)	0.25	.25	.50	98.2%
	0.3	.2	.40	89.0%
120 (for the whole group)	0.25	.25	.50	99.9%
	0.3	.20	.40	99.5%
	0.35	.15	.30	91.6%

Power is for a two sided test with Type I error of 0.05

After enrollment of 32 infants in the Phase II study, it was recognized that there was difficulty in recruiting infants in the lowest GA stratum. The data monitoring committee (DMC) recommended:

- a. Re-distribution of sample size for the study (n=120) between the two higher GA strata (60 infants per stratum compared to previous sample size of 40 infants per stratum). This will allow retention of power of the sample size calculations in the original proposal for analysis in the margins.
- b. Aim to enroll additional 10-20 at least (maximum 40) patients in the lowest GA stratum to address feasibility of study intervention in this group and generate hypothesis for effect size estimate for efficacy in this stratum.

On July 21, 2016, we submitted a clarification amendment to the IRB requesting continued enrollment in Stratum I upto a maximum of 40 subjects as originally proposed till the enrollment targets for the higher two GA strata were met (approved 07-29-2016). This was based on our enrollment patterns, making it seem unlikely that we would reach our enrollment targets ahead of the timeline (30-36 months for study accrual) in the three GA strata.

In Dec 2016, we attained accrual goals for the two higher GA strata. We observed a change in enrollment patterns in the last 5 months of 2016 - we were able to enroll more infants overall and specifically more infants in Stratum I. Since we had several more months available for patient accrual on this grant, we requested an amendment allowing us to continue enrollment in the lowest stratum till Dec 09, 2017 for a maximum of 40 subjects in this stratum, whichever comes earlier. Since Stratum I subjects are most likely to benefit from this intervention, having as much data as possible about feasibility and efficacy in this GA group will be valuable in designing the future definitive Phase III randomized controlled trial.

This amendment was discussed with the FDA grant officer who recommended (02-17-2017) proceeding with amendment submission to IRB and IND review Division if the DMC concurs.

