Data will be analyzed according to the intention-to-treat principle using SAS and PASW (IBM Inc.). We will report descriptive statistics for demographic, clinical and respiratory support data at baseline and over time for the entire sample and for the 4 dosing schedule groups (Appendix IX [Table M1, M2]). In addition, three subgroup analyses are planned – according to dose regardless of dilution (100 vs. 200 mg/kg), GA strata, nebulizer device using logistic regression incorporating an additional treatment-by-subgroup interaction term.

Analysis plan to address Aim #1 – Safety and Feasibility Assessment: Safety will be assessed by quantifying and comparing the AEs and their severity for the total sample and across the dosage/dilution groups and two types of nebulizers. Indicators include cardiorespiratory responses, blockage of NIV circuit and cerebral oxygen saturation (Appendix IX [Table M5]). Descriptive statistics (mean, standard deviation, proportion, inter-quarter range [IQR]) will be used to quantify these indicators; *confidence intervals will be preferred to hypothesis testing* as considerable imprecision is expected arising from low frequencies of these AEs³. ANOVA or *t*-test (continuous measures) and χ^2 test (categorical variables) will be used for comparative analyses though we may not find statistically significant differences. Paired *t*-test will be used to compare heart rate, respiratory rate, blood pressure, SpO₂, PCO₂, cerebral oxygenation (RCO₂, cFTOE), ACoRN score and nasal exam score before and after AS. These parameters will also be compared between infants who get intubated within 72 hours of study intervention and those who do not; and before and after intubation within subjects that get intubated. Feasibility will be assessed by quantifying and comparing the percentage of infants who tolerate the treatment procedure and responses of the clinical nurses and respiratory therapists on the feasibility questionnaire (Appendix IX [Table M6]). Because of the high inherent variability of these factors and small effect sizes, we do not expect to show significant differences between groups given our sample size. However this information will be useful in making the final decision to proceed with a Phase III RCT.

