A number of secondary outcomes will be assessed using the same methodology. Vital signs, SpO₂, FiO₂, NIV parameters (pressure, rate, flow) and ABG/CBG components (pH, PO₂, PCO₂) will be evaluated before and after study intervention (paired *t*-test) and over time (Longitudinal data analysis). Other secondary outcomes include change in surfactant activity in gastric aspirates, changes in cerebral oxygenation, diagnosis of PDA, need for blood transfusions, postnatal growth, duration of respiratory support, length of hospital stay, and incidence of complications of prematurity including IVH, sepsis, NEC, BPD, pneumonia, ROP, and death. We will describe and compare primary and secondary outcome data overall and by dosing schedule, and in three pre-planned subgroup analyses – by dose regardless of dilution (100 mg/kg vs 200 mg/kg), GA group stratum and nebulizer type, recognizing that we may observe trends of differences between groups without having power to determine statistical significance. We will report dichotomous secondary outcome data as proportions and compare the groups using χ^2 and nonparametric tests. We will report secondary continuous outcome data as mean (SD) for normally distributed data and median (interquartile range [IQR]) for skewed data, and will compare the groups by using parametric (*t*-test, ANOVA) and nonparametric tests (Mann-Whitney U test, Wilcoxon's test) as appropriate. Pairwise group comparisons of the four dosing schedule groups will also be performed, although we may lack power to detect significant differences. In a final posthoc analysis, we will compare infants who received intubation within 72 hours to those who did not to understand risk factors for intubation and their modification by study intervention. This analysis will be presented for the entire group and by dosing schedule group. In *adjusted analyses*, dosing schedule, GA group, nebulizer type, mode of NIV, antenatal steroids, and presence of PDA or IVH will be included as covariates recognizing that these analyses are exploratory and need to be interpreted cautiously. We will consider a p value of <0.05 for statistical significance. Mock tables for the planned analyses are presented in Appendix IX.

Recommendations for statistical analyses by the Data Monitoring Committee (DMC) during the conduct of the trial:

1. Additional factors associated with intubation in enrolled infants – clinical team, time of day/shift, clinical variables (e.g. sepsis, NEC)

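### Section 1.1.12 applies an unadjusted p<0.05 to the secondary, pairwise-schedule and subgroup comparisons, and its exploratory label covers only the covariate-adjusted analyses

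*Combined protocol and SAP*

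**What the plan says.** Section 1.1.8 lists 14 numbered secondary efficacy items, several of which hold more than one outcome or time point. Section 1.1.12 says of them: "A number of secondary outcomes will be assessed using the same methodology". Early in the same section it states that "three subgroup analyses are planned": by dose regardless of dilution, by gestational-age (GA) stratum, and by nebulizer. The secondary-outcome paragraph repeats these three groupings for both primary and secondary outcomes and then adds: "Pairwise group comparisons of the four dosing schedule groups will also be performed, although we may lack power to detect significant differences". The paragraph's threshold is a single sentence: "We will consider a p value of <0.05 for statistical significance".

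Four other statements bear on how such results would be read:

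- The covariate-adjusted analyses in 1.1.12 are called exploratory and to be read with caution.
- The safety plan in 1.1.12 prefers confidence intervals to tests.
- Section 1.1.10 says the trial is not powered for efficacy and that Phase II trials generally cannot give formal proof of it.
- Sections 1.1.7.4 and 1.1.12 name one primary efficacy outcome, intubation and mechanical ventilation within 72 hours.

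No section names a multiplicity adjustment, a testing order or an error family.

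**The concern.** A reader following 1.1.12 literally would call a secondary or pairwise result with p=0.03 statistically significant. Nothing attached to those comparisons says otherwise. The low-power remarks warn that real differences may be missed. They say nothing about the chance that some differences reach p<0.05 when none exist, and that chance grows with every outcome and contrast added.

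This matters because 1.1.12 (Aim 2) weighs secondary outcomes as well as intubation when comparing the four schedules, and the trial's results are meant to inform Phase III. A chance finding labelled significant could gain undue weight in the discussion of schedule, device or endpoint.

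**Working it through.** **1. The plan's own figure.** Table 13 and its text use a one-sample test: "A sample size of 30 subjects within each dose schedule group will have 81.8% power", against 0.5, and the table footnote says "Power is for a two sided test with Type I error of 0.05". By the arcsine formula, power = Φ(2·|asin√0.5 − asin√0.25|·√30 − 1.96) = Φ(0.5236 × 5.477 − 1.96) = Φ(0.908) = 0.818. The stated 81.8% reproduces. It concerns the test against a fixed rate. The documents give no error rate for the comparisons considered here, so those have to be computed.

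**2. Inputs.** Four schedules of 30 infants, 120 in all (1.1.4.6, Table 10); two-sided 0.05 per test; four groups give 4×3/2 = 6 pairs. All results below assume no true differences.

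**3. Six pairwise tests of 72-hour intubation.** Each test uses z = |p₁ − p₂| / √(p̄(1 − p̄)·2/30), significant if z > 1.96. If the six were independent, the chance of at least one false result would be 1 − 0.95⁶ = 0.265. They share groups, so the rate was simulated with 200,000 runs per row:

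| True intubation rate | At least one p<0.05 |
|---|---|
| 0.25 | 0.199 |
| 0.30 | 0.197 |
| 0.35 | 0.189 |
| 0.40 | 0.197 |
| 0.50 | 0.211 |

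The range is 19–21%, about four times 0.05. With Holm adjustment (smallest p-value compared with 0.05/6 = 0.0083) it falls to about 0.03–0.04.

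**4. All secondary outcomes.** Assume one outcome per item in 1.1.8, so 14 outcomes, and nine contrasts for each: six pairwise, one four-group, one dose, one nebulizer. GA is left out because a real effect is expected. That makes 14 × 9 = 126 tests, with 126 × 0.05 = 6.3 false positives expected. The documents give no correlation between outcomes, so a range is shown:

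| Assumed correlation | At least one, 126 tests | Dose contrast alone, 14 outcomes |
|---|---|---|
| 0 | 0.98 | 0.51 |
| 0.5 | 0.90 | 0.35 |
| 0.8 | 0.67 | 0.20 |

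At correlation 0 the single-contrast figure agrees with 1 − 0.95¹⁴ = 0.512.

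**5. Cross-checks.** A separate simulation of individual infants, without the four-group test (14 × 8 = 112 tests; 5.6 false positives expected), gave 0.98, 0.91 and 0.68 for any difference, and 0.51, 0.36 and 0.19 for the nebulizer contrast alone. With 14 binary outcomes at assumed rates of 2–30%, it gave 0.88–0.98 for any difference and 0.37–0.49 for the nebulizer. The later enlargement of the trial (1.1.10) does not materially change these rates, because they depend on the number of tests and the threshold far more than on group size.

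**The case against.** The strongest reply is that this is a Phase II estimation and dose-finding trial whose plan says so. Section 1.1.10 disclaims formal proof of efficacy and frames the efficacy goal as estimation with stated precision. It also discusses false positives when it mentions relaxing the Type I error rate. There is one primary efficacy outcome, the subgroups are pre-planned, and some secondary items (blood gases and vital signs, air leak, cerebral oxygenation) overlap the safety indicators for which intervals are preferred. This framing stands and limits the severity. It does not tell a reader how to treat a secondary p-value below 0.05, and 1.1.12 does.

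A second reply also stands in part: the 126-test family is a construction. The pairwise sentence does not say which outcomes it covers. The subgroup analyses are specified as logistic regression with an interaction term, whereas the calculation uses main contrasts. Blood gases and vital signs are planned mainly as before/after and longitudinal analyses, and the mock tables in Appendix IX are not in the document. The larger figures are therefore illustrative. The 19–21% needs only the six pairwise tests on the primary outcome.

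Three stronger readings are tempting and are not supported:

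- *A false schedule or device difference is close to certain.* Only the union of all contrasts at low correlation approaches that. The nebulizer contrast alone gives about 0.2 to 0.5.
- *The plan has no exploratory label.* It has one, on the covariate-adjusted analyses. The gap is that it stops there.
- *A chance result will decide the schedule.* Section 1.1.7.3 and Aim 2 of 1.1.12 select on efficacy, adverse effects and tolerance with no p-value rule. Section 1.1.1 relies on a significant dose trend and says pairwise significance is not needed.

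**Conclusion.** The concern holds in a limited form. Section 1.1.12 supplies a significance rule for the secondary, pairwise and subgroup comparisons but nothing that controls or flags false positives among them. The best-supported size is the 19–21% for six pairwise intubation tests, assuming equal schedules, 30 infants each and a true rate of 0.25–0.5. The wider figures (about 0.67–0.98 for any schedule, dose or nebulizer difference; about 0.2–0.5 for dose or nebulizer alone) also rest on the assumed 14 outcomes and on correlations from 0.8 down to 0.

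The consequence is false claims of significance that could colour the choice of schedule or Phase III endpoint. It does not reach the stated selection rules. The tests of intubation against 0.5 are a separate family and are not judged here. The point is worth correcting before analysis, but it does not undermine the design.

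**What to change.** In 1.1.12, replace the blanket threshold sentence with three statements:

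1. Claims of statistical significance at p<0.05 are confined to the primary efficacy outcome tested against 0.5 and to the dose-trend test announced in 1.1.1.
2. All other secondary, subgroup and pairwise comparisons are exploratory and are reported as estimates with 95% confidence intervals.
3. For the six pairwise schedule comparisons of 72-hour intubation, any p-value shown is Holm-adjusted. The adjusted value replaces the raw one, so the two are not shown side by side.

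This extends to the unadjusted comparisons the caution the plan already gives the adjusted ones, and the interval-first approach it already takes for safety. The cost is a change of wording and one standard adjustment. Fewer results can be called significant, and power falls for pairwise tests that the plan already describes as underpowered. No change to data collection or sample size is needed.
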